5.5. Preparation, Handling, Storage and Accountability

1. The Investigator or designee must confirm that appropriate temperature conditions have been maintained during transit for all study drug(s) received and that any discrepancies are reported and resolved before use.
2. Only participants enrolled in the study may receive study drug(s) and only trained site staff may supply or administer study treatments.
3. The Investigator, institution, or head of the medical institution (where applicable) is responsible for study treatment accountability, reconciliation, and record maintenance (i.e., receipt, reconciliation, and final disposition records).
4. Further guidance and information for the final disposition of unused study drug(s) tablets are provided in the Pharmacy Manual.

6. TESTS AND EVALUATIONS

All required observations and schedules are described in more detail in Sections 6.1 through 6.27.

Most study assessments and procedures (including treatment administration) will be performed in cycles, defined as 28-day intervals starting with the date of DAY101 administration at baseline unless otherwise specified in the sub-protocol. In the absence of toxicity, all scheduled visits will occur within windows for the protocol-specified visit schedule. If the patient is unable to have a study assessment within the defined time window due to an event outside of his or her control (e.g., clinic closure or travel restrictions due to COVID-19, personal/family emergency, inclement weather), the assessment should be performed as close as possible to the required schedule.

6.1. Screening

The screening procedures must be conducted within 28 days prior to [REDACTED] unless otherwise noted. Patients who cannot complete the procedures within the screening window may be rescreened as many times as the Investigator deems appropriate. Procedures that were obtained as part of the patient's standard care prior to providing informed consent for this study do not need to be repeated, with the exception of tumor imaging, which must be repeated if the prior imaging does not collect the appropriate sequences required for study as defined in the Imaging Manual.

Screening tests that are completed in the 48 hours prior to start of DAY101 and duplicate [REDACTED] tests according to the Schedule of Activities (see subprotocol(s) for specific schedule(s) of assessments) will be accepted as fulfilling the [REDACTED] assessments. Repeat testing on [REDACTED] is not necessary for this scenario, and results should be recorded in the screening set of eCRFs.

A completed screening form and supportive materials will be sent to the Sponsor or designee when a potential study candidate is identified. Any reports (e.g., pathology report, MRI report) supportive to the screening form must have Protected Health Information (name, date of birth, address, parents' names, medical record number, etc.) removed prior to submission to Sponsor. The site representative will be contacted by either the Sponsor or its designee to 1) confirm eligibility or 2) provide additional information.

Patients who are determined to be screen failures can be rescreened. Rescreened patients will maintain the same unique patient number assigned to them originally by the Sponsor. A revised screening form should be submitted to the Sponsor or its designee for rescreened patients. See the Study Binder for enrollment form, patient number assignment, contact numbers, and other details of enrollment.

The approved screening form will be returned to the site with the cohort assignment (if applicable) as verification of eligibility in the trial, and for record-keeping purposes.

6.2. Enrollment

Enrollment procedures will be conducted in accordance with the Schedule of Activities (see subprotocol(s) for specific schedule(s) of assessments). Patients who meet the eligibility

criteria, as outlined in each sub-protocol, will be enrolled in this study. Procedure details, timing and details regarding assessments can be found in the Schedule of Activities in each relevant sub-protocol.

6.3. Medical History and Malignancy History

Medical, surgical, and malignancy history, including histologic confirmation of tumor, primary tumor diagnosis and recurrence dates, prior treatments, treatment dates, tumor responses, etc., should be recorded on the appropriate eCRF. Demographics, including age, sex, race, and ethnicity, will be recorded.

6.4. Archival Tumor Samples

See each sub-protocol.

6.5. Freshly Acquired Tumor Samples for Pharmacodynamic Analysis

See each sub-protocol.

6.6. Circulating Tumor DNA (ctDNA) Samples: Blood

For circulating tumor DNA (ctDNA) sample collection regimen and schedule, please refer to sub-protocols.

6.7. Physical Examination

Physical examinations will also include review of systems (neurological, chest, extremities, genitourinary, head/ears/eyes/nose/throat, lymph nodes, musculoskeletal, pulmonary, and skin) during screening, prior to the start of each new cycle, at EOT, and at safety follow-up. Symptom-directed physical examination, including measurement of weight and height, may be performed at other time points after screening per the Schedule of Activities in each sub-protocol.

Patient's skin discomfort, visual disturbance, and cardiopulmonary symptoms need to be noted during physical examination. If any abnormalities arise, relevant specialist examinations should be performed in a timely manner.

6.8. Eastern Cooperative Oncology Group Status/Lansky Performance Status

The Eastern Cooperative Oncology Group (ECOG) (patients aged 16 years or older) or Lansky (patients aged less than 16 years) Status should be assessed in all patients per the Schedule of Activities in each sub-protocol (See Appendix A).

6.9. Assessment of Change in Pubertal Development (Tanner Stage)

For patients 12 to < 18 years of age, pubertal stage will be measured according to the Tanner Stages before the start of treatment (screening) and yearly thereafter while on active treatment through sexual maturity (Marshall and Tanner 1969, Marshall and Tanner 1970). For female patients, age at menarche will be recorded.

6.10. Vital Signs

Vital signs should include the following:

- Systolic and diastolic blood pressure (BP) (For more information on normal ranges of BP by height and weight refer to Appendix H)
- Heart rate, respiratory rate, oxygen saturation, body temperature

For patients, < 18 years of age, blood pressure should be taken manually (auscultatory method) using an appropriate-sized cuff for the patient's arm dimension with feet on the floor. Care should be taken to measure blood pressure prior to other assessments and once child has been calm for a sufficient amount of time. Abnormal blood pressures should be repeated. If (automated) oscillometric methods must be used, then abnormal values should be confirmed with a manual measurement.

6.11. Ophthalmology Examination

See Sub-Protocol DAY101-102a and Sub-Protocol 102b.

6.12. Visual Symptom Assessment

See Sub-Protocol DAY101-102a and Sub-Protocol 102b.

6.13. Dermatologic Examination

A baseline dermatologic examination of the entire skin should be performed by the Investigator and/or a dermatologist. The initial examination by the Investigator/dermatologist should include a complete dermatological history of prior medications and cutaneous squamous cell carcinoma (SCC) risk factors (i.e., radiation therapy, sun exposure, immunosuppression, prior SCC, use of tanning beds, precursor lesions, and photochemotherapy for psoriasis).

Subsequent examinations should be symptom-directed and as clinically indicated and should be assessed by the Investigator and/or a consulting dermatologist for skin lesions, especially for keratoacanthomas and squamous cell carcinomas.

For each skin lesion observed, the dimensions and location on the body will be recorded. Existing lesions will be monitored throughout the study, and changes to the lesions should be recorded in the eCRF. Lesions developing during therapy that are suspected keratoacanthomas or squamous cell carcinomas will be biopsied and adequately treated; other lesions may be biopsied per the discretion of the Investigator/dermatologist. Any new or worsening skin lesions or rashes should be reported as adverse events.

Melanoma patients with clinical lesions followed for response please refer to Appendix B for additional details.

Recommended prophylactic skin care regimen and management options for rashes is available in each sub-protocol. It is recommended all patients receiving study drug follow the prophylactic skin care regimen.

6.14. Neurologic Examination

A baseline complete neurologic examination should be performed by the Investigator and/or a neurologist. Symptom-directed neurologic examinations may be completed at subsequent visits.

6.15. Height and Bone Age

Patients 12 – 18 years (inclusive) should have changes in height compared to standard growth curves to monitor potential effects on bone growth.

Patients 12 – 18 years (inclusive) will have a bone age assessment via bone age radiograph of the left wrist during screening. Patients without epiphyseal closure at the time of screening will have a bone age left wrist radiograph performed every 6 months to monitor for the potential risk of growth retardation.

6.16. Cardiac Function

6.16.1. Electrocardiograms

Twelve-lead resting electrocardiogram (ECGs) will be performed in triplicate per the Schedule of Activities in each sub-protocol. To minimize variability, it is important that patients be in a resting position for at least 5 minutes prior to each ECG evaluation. Body position should be consistently maintained for each ECG to prevent changes in heart rate. ECGs for each patient should be obtained from the same machine whenever possible. Any clinically significant changes in ECGs that occur during the study should be reported as AEs in the eCRF.

6.16.2. Echocardiogram/Multiple-Gated Acquisition

Echocardiogram (ECHO) or multi-gated acquisition (MUGA) will be performed per normal site protocol. The choice of ECHO or MUGA is left up to the Investigator, but the same technique should be used for each patient for each evaluation period. Any clinically significant changes in ECHO/MUGA that occur during the study should be reported as AEs in the eCRF.

6.17. Laboratory Tests

For pediatric/adolescent patients (aged < 18 years), blood volumes drawn will be minimized, in accordance with the European Commission (EC)'s recommendations, "Ethical considerations for clinical trials on medicinal products conducted with the pediatric population" (2008) and "Ethical considerations for clinical trials on medicinal products conducted with minors" (2017).

Routine laboratory tests will be performed locally. Special assessments such as PK will be performed centrally or as individually indicated. Additional information on the handling and processing of PK samples is provided in the separate Laboratory Manual.

6.17.1. Pregnancy Test

Urine or serum pregnancy tests are required for women of childbearing potential (surgically sterilized female patients or those who have not experienced menses for at least 2 years are not required to be tested). If any urine pregnancy test is positive, study treatment will be delayed until the patient pregnancy status is confirmed by a serum pregnancy test. If the serum pregnancy test is positive, the patient will be permanently discontinued from study treatment. Pregnancy reporting information is provided in Section 8.1.5.

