8.1.5. Pregnancy or Combination Partner

There is no relevant clinical experience with DAY101 (as a single agent or in combination) in pregnant or lactating female patients, and animal reproductive studies have not been performed. Women of childbearing potential must have a negative pregnancy test prior to enrollment because of the potentially dangerous effects of the preparative chemotherapy on the fetus. This experimental therapy should not be administered to pregnant women or women who are breastfeeding.

- Details of all pregnancies in female patients and female partners of male patients will be collected for pregnancies occurring after the start of study intervention until 6 months after completing DAY101.
- If a pregnancy is reported, the Investigator should inform the Sponsor within 24 hours of learning of the pregnancy and should follow the procedures outlined in Appendix F.
- If a lactation case is reported, the Investigator should inform the Sponsor within 24 hours of learning of the lactation case and should follow the procedures outlined in Appendix F.
- Abnormal pregnancy outcomes (e.g., spontaneous abortion, fetal death, stillbirth, congenital anomalies, ectopic pregnancy) are considered SAEs.

In addition to reporting any pregnancies or lactation cases occurring during the study, Investigators should monitor for pregnancies or lactation cases that occur after the last dose of DAY101 through 6 months for female patients and for 6 months for female partners of male patients.

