Appendix E: List of Research Uses of Tissue, Plasma and Clinical Data

Appendix F: Contraceptive Guidance and Collection of Pregnancy Information

Definitions:

Woman of Childbearing Potential (WOCBP)

A woman is considered to be fertile following menarche and until becoming postmenopausal, unless permanently sterile (see below).

If fertility is unclear (e.g., amenorrhea in adolescents or athletes) and a menstrual cycle cannot be confirmed before first dose of study intervention, additional evaluation should be considered.

Women in the following categories are not considered WOCBPs:

- Premenarchal
- Premenopausal woman with one of the following:
 - Documented hysterectomy
 - Documented bilateral salpingectomy
 - Documented bilateral oophorectomy
 - For individuals with permanent infertility due to an alternate medical cause other than the above (e.g., Müllerian agenesis, androgen insensitivity), Investigator discretion should be applied to determining study entry.

Note: Documentation can come from the site personnel's review of the patient's medical records, medical examination, or medical history interview.

Contraception Guidance:

Male patients are not allowed to donate sperm during the course of this study or within 180 days after receiving their last dose of study drug.

Female and male patient of reproductive potential must agree to avoid becoming pregnant or impregnating a partner, respectively, while receiving study drug(s) and for 180 days after the last dose of study drug(s) by complying with one of the following:

(1) practice abstinence† from heterosexual activity;

OR

(2) use two acceptable methods of contraception in which one method must be a barrier (a condom is preferred) in addition to one of the highly effective contraception methods described below during heterosexual activity.

Acceptable methods of highly effective contraception methods with a failure rate of less than 1% per year are‡:

- Combined estrogen- and progestogen-containing hormonal contraception associated with inhibition of ovulation given PO, intravaginally, or transdermally
- Progestin-only hormonal contraception associated with inhibition of ovulation given PO, by injection, or by implant

- Intrauterine device (IUD)
- Intrauterine hormone-releasing system (IUS)
- Bilateral tubal occlusion or ligation
- Vasectomized partner

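### The pregnancy-test waiver in Section 6.17.1 covers anyone without menses for 2 years, whatever the cause; for a narrow group this conflicts with Section 8.1.5 read with Appendix F

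*Protocol*

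**What the plan says.** Protocol Section 6.17.1 (Pregnancy Test) makes urine or serum tests mandatory for women of childbearing potential and qualifies this in a parenthesis: "surgically sterilized female patients or those who have not experienced menses for at least 2 years are not required to be tested". It then sets out what follows a positive result: "If any urine pregnancy test is positive, study treatment will be delayed until the patient pregnancy status is confirmed by a serum pregnancy test". A positive serum test leads to permanent discontinuation of study treatment.

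Appendix F defines childbearing potential: "A woman is considered to be fertile following menarche and until becoming postmenopausal, unless permanently sterile". It gives no duration of amenorrhea for menopause. It also describes a doubtful case, "If fertility is unclear (e.g., amenorrhea in adolescents or athletes) and a menstrual cycle cannot be confirmed before first dose of study intervention", for which it advises considering further evaluation. Its list of women who are not of childbearing potential has these entries: premenarchal; premenopausal with a documented hysterectomy, bilateral salpingectomy or bilateral oophorectomy; and an item left to Investigator discretion, "For individuals with permanent infertility due to an alternate medical cause other than the above". Tubal ligation is not on that list. It appears among the contraceptive methods, as "Bilateral tubal occlusion or ligation".

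Section 8.1.5 states: "Women of childbearing potential must have a negative pregnancy test prior to enrollment". It makes no exception for amenorrhea. On the nonclinical background it says that "animal reproductive studies have not been performed".

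**The concern.** The 2-year limb of the waiver was probably meant as a stand-in for menopause, but the words do not say so. As written, it also reaches a patient who has stopped menstruating for another reason, or for no known reason, and who may still be fertile. The master protocol enrolls from age 12 (Section 3.1) and records Tanner stage and age at menarche (Section 6.9). Appendix F itself names adolescents and athletes with amenorrhea as doubtful cases, so the sponsor has already foreseen amenorrhea that is not menopause.

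The stake is detection. The delay and discontinuation steps in Section 6.17.1 start from a positive test, so they cannot start for a patient who is never tested. A pregnancy present at enrollment could be missed, or one arising later could be found late, on a drug without animal reproductive studies.

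**Working it through.** No calculation applies, and the plan states no figure to reproduce. The check takes each kind of patient through the two texts.

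| Patient | Section 6.17.1 | Appendix F | Agree? |
|---|---|---|---|
| Premenarchal | Exempt on a literal reading (no menses) | Not of childbearing potential | Yes |
| Postmenopausal, 2 or more years without menses | Exempt | Not of childbearing potential | Yes |
| Hysterectomy, bilateral salpingectomy or bilateral oophorectomy | Exempt if read as surgical sterilization | Not of childbearing potential | Yes |
| Tubal ligation | Exempt if read as surgical sterilization | Listed as contraception, not as a reason for non-childbearing status | Unclear |
| Post-menarchal, non-menopausal, 2 or more years of amenorrhea, no permanent sterility | Exempt | Of childbearing potential, or of unclear fertility | No |

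**The last row.** Appendix F offers these ways out of childbearing potential: postmenopausal status in the definition sentence (1), premenarchal status (1), three operations (3), and the discretionary item on other permanent infertility (1). That is 1 + 1 + 3 + 1 = 6. The last is arguable, because the discretion there concerns study entry; without it the count is 5. On either count, none covers this patient. The count only confirms that no listed route was overlooked. It does not measure impact.

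**The link to Section 8.1.5.** Taken alone, Section 8.1.5 does not contradict Section 6.17.1, since both speak of women of childbearing potential. The conflict appears once Appendix F supplies the definition. The patient in the last row is then either a woman of childbearing potential, who needs a negative test before enrollment, or a doubtful case for evaluation. Section 6.17.1 tells the site that no test is needed.

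**Can the 2-year figure be read as the missing duration for menopause?** Appendix F states none, so the reading is natural. It settles the menopausal row only. The waiver is not limited to menopausal patients, so the last row remains.

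**Can the parenthesis be read as explaining who lacks childbearing potential?** If so, it is a second definition that differs from Appendix F, and the same patient is still classified in two ways.

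**The case against.** The strongest reply is that the texts can be followed together. Appendix F contains no testing rule, so it cannot directly contradict a testing waiver. Not requiring a test does not forbid one, and a site that tests this patient breaches nothing. That is correct. It limits the finding to a conflict over what is required, reached by reading three sections together. It does not remove the conflict, because a site that relies on the waiver also complies with Section 6.17.1.

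A reader might infer that a pregnant patient in this group would be left on treatment with no protection. The documents do not support that:

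- Section 5.3 lists pregnancy as a reason for discontinuing treatment, with no link to a scheduled test.
- Appendix F takes any patient who becomes pregnant during the study off study intervention, however the pregnancy is found.
- Appendix F asks patients of reproductive potential to abstain or use two contraceptive methods, one of them a barrier, during dosing and for 180 days afterwards. The definition that puts this patient in the gap also puts her under that rule.

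What stands is a possible missed or late detection.

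A reader might also infer that such patients do go untested. That cannot be shown. Eligibility criteria and schedules are in sub-protocols that were not available. The pregnancy-test row of SAP Table 2 carries footnote n, but the footnotes in the text available stop at i. Either source may set a stricter rule. The Sponsor or its designee also confirms eligibility (Section 6.1). Nor do the documents show that any patient of this kind has enrolled or will.

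Finally, the practical reach is limited. The SAP (Section 2.2.1) records the early termination of sub-study 102a. A change would mainly serve 102b, which Section 6.11 names but whose status is not given.

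**Conclusion.** The inconsistency is real and narrow. Section 6.17.1 waives testing for a post-menarchal, non-menopausal patient with 2 or more years of amenorrhea and no permanent sterility. Section 8.1.5 read with Appendix F requires a negative test if she counts as being of childbearing potential, and Appendix F advises considering evaluation if her fertility is unclear. The consequence is a possible missed or late detection of pregnancy, with the other safeguards in place.

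Severity is minor and confidence medium. No number of patients or missed tests is claimed, because the documents give no basis for one. The efficacy analyses are unaffected. The conclusion rests on the master protocol's current wording and assumes that no sub-protocol overrides it.

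**What to change.** 1. In Section 6.17.1, replace the parenthesis with: *patients who are not women of childbearing potential as defined in Appendix F need not be tested*.
2. In Appendix F, add to the non-childbearing list: *Postmenopausal: no menses for at least 2 years that the Investigator attributes to menopause; amenorrhea of another or unknown cause does not qualify*. This keeps the protocol's own 2-year figure. The attribution to menopause is needed because an entry resting on duration alone, or on duration with no other cause found, would again exempt a young patient with unexplained amenorrhea.
3. Decide on tubal ligation. Appendix F treats it as contraception, so step 1 alone would bring those patients into testing. To keep the present exemption, state in Section 6.17.1 that patients with documented surgical sterilization remain exempt, and make the same exception in Section 8.1.5 so that the two agree.

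The cost is a short wording amendment, which Section 9.1.2 requires ethics committees to approve before it is implemented, and a few extra urine tests of a kind the trial already performs. Premenarchal patients and menopausal patients with 2 years without menses stay exempt.
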